4.5 Informed Consent

Informed consent/assent. The informed consent process will occur on the day the enrollment visit is held. Consent may be done online, in person, or over the phone. A teleconference platform such as Zoom (see Section 7.3.6 for description of the Zoom platform) or other comparable platform will be used for online study visits and consenting. Interested persons will be guided through the informed consent process by study staff, who will explain all study procedures, answer questions concerning the study and consent process, and offer a copy of the informed consent/assent form. The research staff member will give the participant as much time as needed and will address any questions or concerns they may have. The participant will be allowed to take the consent/assent form home and review it before enrolling in the study if the participant needs more time to review the form. The research staff member will ask the participant questions to gauge comprehension. The consent/assent form describes all study procedures, including confidentiality and privacy, information about potential risks, discomforts, benefits of participation, and information regarding who they can contact with further questions. It also states that participation is voluntary, that participants may decide not to take part or to withdraw from the study at any time without penalty or loss of any benefit to which they might otherwise be entitled, and that study participation is in no way related to being able to access or continue getting care or services at any participating study site. Participants can refuse to answer any question, and can withdraw from the study at any time. The PIs, Co-PIs, or designee at each site will review all informed consents and assents. The informed consent/assent form may be on paper or online

via a HIPAA-compliant, secure online platform, such as Alchemer or Qualtrics (see Section 7.3.7 for details on Qualtrics).

Assessing for decisional capacity. For all participants, the research assistant (RA) reviews the informed consent/assent to make an assessment of the participant's decisional capacity and ability to provide consent/assent prior to signing, using a 2-step process. First, the RA determines if the person understands the study goals by asking a question such as, "Can you tell me what this study is about?" In step 2, potential participants will be asked questions designed to assess their capacity to understand, appreciate, reason with, and express a choice about participation in our specific protocol. Participants will be asked to: name things they will be expected to do during the study; explain what they would do if they no longer wished to participate in the study; explain what they would do if they experienced distress during the study; and identify potential risks for participating in the study. For YYA who cannot answer these questions, the RA will go back and review the relevant elements of consent with the participant again and repeat the process. YYA who appear not to understand after repeated review will not be enrolled in the study. If the enrollment process occurs online, research staff will talk with potential participants via phone or online teleconference platform such as Zoom (see Section 7.3.6 for description of the Zoom platform) or other comparable platform to assess for decisional capacity and to address any questions or concerns the person may have.

Waiver of parental consent. We will request that the UNC-CH IRB as the central IRB (IRB of Record) grant a waiver of parental consent to participate in this research study for youth participants who are 15 to 17 years of age. The research team has been granted waivers of parental permission for prior studies with sexual minority youth. Under 45 CFR 46.408 (c), an IRB has the authority to waive parental permission if it determines that "a research protocol is designed for conditions or a subject population for which parental or guardian permission is not a reasonable requirement to protect the subjects" and "an appropriate mechanism for protecting the children who will participate as research subjects is substituted" and "that the waiver is not inconsistent with Federal, State, or local law." A waiver of signed consent and parental/legal guardian permission will be sought given that minor individuals can often seek sexually transmitted infection (STI) and HIV testing without parental/legal guardian permission, depending on each site's state laws, and given that many of the trans youth in our study are likely to be gender and/or sexually fluid or have an attraction to persons of the same gender, but may not be "out" to their parents; requiring parental permission may place participants at risk for disclosing as part of the LGBT community or being at risk for HIV infection. A waiver of parental permission for studies with LGBT youth that do not involve greater than minimal risk is a common practice among researchers working in the area of gay and lesbian health/mental health. This is done to avoid the selection biases operating in only recruiting youth whose parents are both aware of and comfortable with their sexual or gender identity. Commonly, these youth have explored their sexuality or gender expression without their parents' knowledge as the youth struggle with issues of disclosure and its consequences within the social, religious, and economic context of their families. A requirement for parental permission in this type of study could not only affect a person's willingness to participate, but could also potentially impact the ability of researchers to engage in this type of research with gender and sexual minority youth.

If the purpose of requiring parental permission as stated in CFR is to protect the minor subject, then requiring parental permission for youth in these circumstances is not a reasonable requirement. Additional privacy protections are provided in that all assessments, notes, reports, and other records will be identified by only a coded number to maintain participant confidentiality. These records and any forms that do contain identifying information (e.g., consent/assent forms,

contact information) will be kept in a locked, limited access area (such as a locked file cabinet) at the participating site.

5.0 STUDY PROCEDURES

5.1 Enrollment Procedures

5.1.1 Focus group enrollment

Screening procedures are explained above in section 4.4. All persons who screen eligible for the study will be guided through the informed consent process (section 4.5) on the day the focus group is held. Research staff administering the consent process will pay particular attention to whether the potential participant appears confused or otherwise unable to complete the informed consent process, and will stop enrollment of that participant in the focus group.

Following informed consent, trans YYA will be walked to the focus group room where they will complete a brief paper-and-pencil Focus Group Participant Survey (e.g., additional demographics and technology use survey) before the focus group begins. After informed consent/assent is obtained and the Focus Group Participant Survey is completed, participants will be deemed enrolled in the study.

Participants will be compensated for their time once the focus group has ended. Participants who leave the focus group early will be compensated the same amount regardless of how long they are present.

5.1.2 RCT Enrollment

Screening procedures are explained above in section 4.4. All persons who screen eligible for the study will be guided through the informed consent process (section 4.5) on the day of their enrollment appointment. Research staff administering the consent process will pay particular attention to whether the potential participant appears confused or otherwise unable to complete the informed consent process, and will stop enrollment of that participant in the RCT.

Following informed consent, trans YYA will go through baseline assessment procedures of having HIV testing, blood microsampling analysis for those who self-report PrEP use, screening for STIs and drug use through a urine screen (note: HIV testing is the only required biological specimen collection, all others are voluntary), and the survey measures through an ACASI. Biological specimen collection may be done in person during the study visit or via self collection kits mailed to participants. For mailed self collection, the biological specimens may be collected after the baseline enrollment visit and must be returned within 90 days. After randomization, participants will receive more information about the arm they are randomized into (e.g. how to use the WebApp, the frequency of text messages, or how to access the resources and information). For in person enrollment visits, participants will be deemed enrolled in the study after baseline procedures and the enrollment visit are completed. For online enrollment visits, participants will be deemed enrolled in the study after they are randomized and onboarded.

5.2 Randomization Procedures

For the purpose of Phase 1 focus groups, participants will not be randomized.

Randomization for the RCT is explained in section 3.3.2.

During the RCT, after completion of the baseline ACASI, participants will be randomized 1:1:1 to the Text+Step intervention or App+Step intervention or control condition, based on a randomization sequence developed by the AC lead statistician and loaded into DFexplore (see section 7.4.1 for more details on DFexplore). The randomization sequence will be stratified by city and use random permuted blocks of size 3.

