QNS	Query and Notification System
RCG	Radiant Creative Group
RCT	Randomized Controlled Trial
RDC	Remote Data Capture
SRV	Subject Recruitment Venue
SSL	Secure Sockets Layer
TC	Technology Core
Trans	transgender feminine, transgender masculine, gender non-conforming
TWM	Thrive With Me
UMN	University of Minnesota
VL	Viral Load
YAB	Youth Advisory Board
YLWH	Youth Living With HIV
YO	Years Old
YT	Youth Thrive
YYA	Youth and Young Adults

STUDY ABSTRACT

DESIGN:	TechStep is a three-arm, technology-based randomized controlled trial (RCT), with a stepped care approach, among high-risk HIV-negative trans youth and young adults (YYA) for reducing sexual risk behaviors and increasing PrEP uptake.
DURATION:	Trans YYA are enrolled for 9 months in the RCT.
SAMPLE SIZE:	Total study sample is 355 of which the following will be enrolled for each phase: 1) up to 80 participants for focus groups to inform intervention adaption; 2) 275 participants for a randomized controlled trial of TechStep, with participants randomized to either text messaging stepped care (n=108), WebApp stepped care (n=83) or control (n=83) condition.
POPULATION:	Participants will include YYA who are self-identified trans feminine, trans masculine or gender non-conforming or whose birth sex and current gender do not match; ages 15 to 24 years; HIV-negative; and sexually active. For Phase 1, participants must self-report never having received a positive HIV test result; participants age 15-20 must report any kind of sex in the previous 12 months, while participants age 21-24 must report vaginal or anal sex (either insertive or receptive; excluding sex toys) in the previous 12 months. For Phase 2, participants must have a confirmed HIV negative serostatus and report anal or vaginal sex (either insertive or receptive; excluding sex toys) in the previous 12 months. For Phase 2, participants will be recruited from SRVs in Houston, Los Angeles, New York City, Philadelphia, and Boston.
STRATIFICATION:	Focus group discussions will be stratified by age (50% 15-20 years old; 50% 21-24 years old).
DATA COLLECTION:	Focus group discussions will be conducted in-person, digitally recorded, and professionally transcribed. There will be five data collection (screening, baseline, 3-month, 6-month, and 9-month) time points for the RCT. Visits will

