be conducted in-person at the SRV, online, or some combination of in person or online. The ACASI will be completed using online survey tools. An HIV test, STI panel, urine screen for recent illicit drug use, and blood microsampling, for those who report PrEP uptake, to verify PrEP adherence will be collected in-person at the participant's SRV or via mailed self-collection kits. HIV testing during enrollment is mandatory, and encouraged during follow-ups. All biological specimen collection with the exception of HIV testing at enrollment is optional but encouraged. Process data of participant activity at each step of the intervention, as well as the control intervention, will be collected.

OBJECTIVES:

Primary Aim 1: Conduct formative research to develop the stepped care (text messaging, WebApp, and eCoaching) interventions and refine iterations through input from focus groups with trans YYA at the four study sites (n=80) and a youth advisory board (YAB).

Primary Aim 2: In a 3-arm RCT (N=275), assess the differential immediate and sustained effects of a low intensity information (“Info”) arm compared to a text messaging stepped care intervention (text messaging plus step to eCoaching for YYA with continued high risk) arm compared to a WebApp stepped care intervention (WebApp plus step to eCoaching for YYA with continued high risk) arm for reducing sexual risk behaviors and increasing PrEP uptake among high-risk, HIV-negative trans (15-24 years old).

Secondary Aim 3: Determine the added benefit of text messaging plus eCoaching versus text messaging alone and of WebApp plus eCoaching versus WebApp alone for reducing sexual risk behaviors and increasing PrEP uptake.

[figure not shown]
Secondary Aim 4: Assess the differential immediate and sustained effects of low intensity information compared to text messaging only compared to WebApp only for reducing sexual risk behaviors and increasing PrEP uptake.

Secondary Aim 5: Determine the impact of structural- (e.g., transphobia, housing insecurity, educational attainment, access to healthcare) and individual-level (e.g., identity formation, gender transition, gender expression,

stigma, discrimination) trans-specific factors as moderators of intervention outcomes.

STUDY DESIGN OR SCHEMA

Figure 1. TechStep Study Design

Note: Text arm increasing from 83 to 108 as of February 2021.

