2.0 STUDY OBJECTIVES

Primary Aim 1: Conduct formative research to develop the stepped care (text messaging, WebApp, and eCoaching) interventions and refine iterations through input from focus groups with trans youth and young adults (YYA) at the four study sites (n=80) and a youth advisory board (YAB).

Primary Aim 2:

In a 3-arm RCT (N=275), assess the differential immediate and sustained effects of a low intensity information (“Info”) arm compared to a text messaging stepped care intervention (text messaging plus step to eCoaching for YYA with continued high risk) arm compared to a WebApp stepped care intervention (WebApp plus step to eCoaching for YYA with continued high risk) arm for reducing sexual risk behaviors and increasing PrEP uptake among high-risk, HIV-negative trans (15-24 years old).

Hypothesis 1a: There will be significantly greater reductions in sexual risk behaviors among those in the Text+Step and App+Step arms compared to the low intensity Info arm.

Hypothesis 1b: There will be significantly greater uptake of PrEP among those in the Text+Step and App+Step arms compared to the low intensity Info arm.

Secondary Aim 3:

Determine the added benefit of text messaging plus eCoaching versus text messaging alone and of WebApp plus eCoaching versus WebApp alone for reducing sexual risk behaviors and

increasing PrEP uptake.

Secondary Aim 4: Assess the differential immediate and sustained effects of low intensity information compared to text messaging only compared to WebApp only for reducing sexual risk behaviors and increasing PrEP uptake.

Secondary Aim 5: Determine the impact of structural- (e.g., transphobia, housing insecurity, educational attainment, access to healthcare) and individual-level (e.g., identity formation, gender transition, gender expression, stigma, discrimination) trans-specific factors as moderators of intervention outcomes.

Hypothesis 2: Structural- and individual-level trans-specific factors will moderate intervention outcomes, such that participants who report higher amounts and degrees of these factors will require more intensive intervention steps (i.e., eCoaching).

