3.2 Study Population

We propose to enroll 355 trans YYA for the purposes of this study. Up to 80 participants will be recruited for focus group discussions (with the goal of 5-7, a minimum of 3 and a maximum of 10 per group), and 275 participants (n=108 Text+Step, n=83 App+Step and n=83 control) will be recruited to participate in the TechStep RCT.

Inclusion criteria for the focus groups and RCT are described in Section 4.0 (note: the Youth Advisory Board members are not considered human subjects for research and, therefore, inclusion criteria are not listed for YABs).

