3.3.2 RCT

In the RCT, participants will be randomized 1:1:1 to the Text+Step intervention or App+Step

intervention or control condition. Randomization procedures are further explained in Section 5.2.

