10.2.2 RCT Power Considerations

We performed extensive Monte Carlo simulations to assess the power for our primary analysis. We examined scenarios involving different dropout rates (5-15%), different relative efficacies of first-line (text or app) interventions relative to the eCoaching intervention, and different levels of strength of predictive covariates to be included in the analysis. Across a wide range of scenarios, we determined that we will have >80% power to detect a clinically meaningful effect, defined as an average decrease of at least 1.5 risky sexual encounters over the course of the study.

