10.3.2 Analyses of RCT

Outcomes under study include rates of condomless anal and vaginal sex, number of exchange partners, reports of sex while feeling the effects of stimulants (i.e. methamphetamine, powder cocaine, crack cocaine) or after binge drinking (5+ drinks at one time), self-report and confirmed STI diagnoses, and PrEP adherence measured through self-report and verified by blood microsampling. We will analyze both the primary and secondary questions in the RCT using longitudinal targeted minimum loss-based estimation (LTMLE).³⁸ This approach has several advantages over standard techniques for longitudinal data analysis. First, it appropriately accounts for the fact that only high-risk participants are eligible for randomization into the eCoaching intervention. Second, the method accounts for predictive and prognostic time-varying participant-level covariates, thereby increasing the power to detect intervention effects. Third, the method accounts for possibly informative missingness reducing bias in the estimates of causal effects. Implementation of LTMLE involves fitting several covariate adjusted models. First, a sequence of regressions are fit to model cumulative sexual risk behaviors at each time point adjusting for baseline and time-varying covariates. Second, a regression is fit to model the cumulative probability of participant dropout adjusting for baseline and time-varying covariates. These models will be fit using the super learner, a cross-validation-based estimator selection technique. This method aggregates results from a library of candidate regression estimators to build the most powerful predictor given the data at hand. In large samples, the method is guaranteed to perform as well as the unknown best-performing regression in the library. We will use Wald-style tests of each of the relevant null hypotheses using cross-validated influence-function-based standard error estimates.

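### The stated 1:1:1 randomisation in blocks of 3 within city cannot give the planned 108/83/83 arms, and the plan does not say how the added Text participants are assigned

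*Combined protocol and SAP*

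**What the plan says.** Two sections give the allocation rule. Section 3.3.2 states that "participants will be randomized 1:1:1 to the Text+Step intervention", the App+Step intervention or control. Section 5.2 repeats the ratio and adds: "The randomization sequence will be stratified by city and use random permuted blocks of size 3". Section 5.3.3 lists five enrolling sites, each in a different city.

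Two places give the arm sizes. The abstract has "participants randomized to either text messaging stepped care (n=108), WebApp stepped care (n=83) or control (n=83) condition", and section 3.2 has "275 participants (n=108 Text+Step, n=83 App+Step and n=83 control) will be recruited to participate in the TechStep RCT". The note under Figure 1 reads: "Note: Text arm increasing from 83 to 108 as of February 2021".

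On analysis, section 10.3.2 says that "a sequence of regressions are fit to model cumulative sexual risk behaviors at each time point adjusting for baseline and time-varying covariates", followed by a regression for dropout. It names no covariate and gives no probability of assignment to arm. Section 10.2.2 defines the effect of interest as "an average decrease of at least 1.5 risky sexual encounters over the course of the study".

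**The concern.** The allocation rule and the arm sizes are both current text, and they contradict each other. The rule fits the old target of 83 per arm but not the new one. The plan gives no revised ratio, no new block scheme and no count of participants randomised before February 2021. It also does not say whether App+Step and Info kept enrolling. A reader therefore cannot tell how participants reached the primary arms.

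The second issue is conditional. If some participants were randomised 1:1:1 and later ones at a ratio favouring Text, the Text arm holds a larger share of late enrollees than Info or App. Any change over time in the mean outcome would then enter the Text comparisons. Such a change is plausible but not shown: the outcomes are self-reported sexual behaviour and PrEP use, and section 4.4 describes visits moving between in-person and online because of the pandemic. Text+Step versus Info is in both primary hypotheses (1a and 1b), and Aim 2 also compares Text+Step with App+Step. App+Step versus Info is not affected if those two arms kept equal allocation.

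**Working it through.** **1. Can the stated rule give the stated arms?**

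Each complete block of 3 puts one participant in each arm. Only the last, incomplete block in a city can create imbalance, and then by at most 1 between any two arms. Over five cities the largest possible difference is 5 × 1 = 5. The plan needs 108 − 83 = 25.

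Text is largest when all five cities end with one leftover participant and all five go to Text: (275 − 5)/3 = 90 complete blocks, so Text = 90 + 5 = 95. Full enumeration of the leftover patterns gives a feasible Text range of 89 to 95 at N = 275, and 88 to 94 at N = 274. In 20,000 simulated allocations (N = 274, five equally likely cities) the difference never exceeded 5.

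Other checks on the figures:
- The old target is consistent with the rule: 3 × 83 = 249, which divides evenly 1:1:1.
- Equal allocation of 275 gives 275/3 = 91.7 per arm, which is neither 108 nor 83.
- Without any blocking, the probability of 108 or more in Text out of 274 under 1:1:1 is 0.020.
- 108 + 83 + 83 = 274, not 275.

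**2. Bias if the ratio changed part-way and period is ignored**

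Let m be the number per arm randomised 1:1:1 before the change. The plan does not give m, so the full range is shown. Assume that the final arms are 108/83/83.

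- Late share in Text: 1 − m/108. Late share in Info: 1 − m/83.
- Multiplier = m/83 − m/108 = m × 25/(83 × 108) = 0.00279m.
- Bias in Text versus Info = multiplier × (late mean outcome − early mean outcome).
- Text:Info ratio after the change = (108 − m)/(83 − m).

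**3. Cost of adjusting for period**

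An additive period term removes an additive shift. With equal variances, the ratio of adjusted to unadjusted standard error is √[46.93 / (m/2 + (108 − m)(83 − m)/(191 − 2m))], where 46.93 = 108 × 83/191.

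| m | Text:Info after change | Multiplier | Bias, shift 1.5 | SE increase |
|---|---|---|---|---|
| 0 | 1.30 | 0 | 0 | 0% |
| 20 | 1.40 | 0.056 | 0.08 | 0.2% |
| 40 | 1.58 | 0.112 | 0.17 | 0.6% |
| 60 | 2.09 | 0.167 | 0.25 | 1.5% |
| 83 | Text only | 0.231 | 0.35 | 6.3% |

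At m = 80 the SE increase is 4.8%.

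The shift of 1.5 is an assumption, borrowed from the effect size in section 10.2.2 for scale. Over an assumed range of 0.5 to 3 encounters, the bias at m = 83 is 0.231 × 0.5 = 0.12 to 0.231 × 3 = 0.69, or 8% to 46% of 1.5. At m = 60 it is 0.167 × 0.5 = 0.08 to 0.167 × 3 = 0.50. For PrEP uptake the same multiplier applies: each percentage point of shift between periods moves the Text versus Info difference by up to 0.23 points.

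A simulation (4,000 runs, additive shift 1.5, assumed SD 4) gave unadjusted bias of 0.00, 0.17, 0.26 and 0.36 for m = 0, 40, 60 and 83. With a period term it was 0.00 to 0.01 throughout.

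**The case against.** The simplest reading is that sections 3.3.2 and 5.2 carry the original rule and were not updated when the Text target rose. On that view the proven fault is stale wording. The missing participant may be rounding.

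Confounding needs three things that the documents do not establish: participants randomised 1:1:1 before the change, a shift in mean outcome between periods, and an analysis that ignores period. The planned LTMLE with super learner adjusts for baseline covariates and could include period.

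The likely bias is also modest against sampling error. With SD 4 and shift 1.5, the standard error of Text versus Info is 4 × √(1/108 + 1/83) = 0.58. The bias at m = 40, 60 and 83 is then about 0.29, 0.43 and 0.60 standard errors, which takes a two-sided 5% test to roughly 6%, 7% and 9%.

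Most of this is fair, and it means the bias must be stated as conditional. It does not remove the point. If the wording is stale, the rule actually used is still unreported. Section 10.3.2 neither names period nor gives an allocation probability, and the only ratio in the plan is one that cannot have produced the planned arms. If the added participants were Text-only, there are no concurrent Info or App participants in that period, and adjustment would rest on extrapolation. The drawing of Figure 1 was not available here, only its note, so the omission is confirmed for the text alone.

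**Conclusion.** The contradiction is certain: the stated rule allows a difference of at most 5 between arms and at most 95 in Text, against the planned 25 and 108. The absence of an assignment rule for the added Text participants is confirmed in the available text. These two facts are what make the correction necessary, whatever the size of the bias.

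The bias is a conditional risk. It is zero if the new ratio applied from the first participant. Otherwise it grows with m, to 23% of the period shift if the 25 additions were Text-only. These figures assume an additive shift, equal numbers per arm before the change, and final arms of 108/83/83.

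**What to change.** 1. Correct sections 3.3.2 and 5.2 to give the ratio, block scheme and dates used before and after February 2021. State whether App+Step and Info stayed open, and give arm sizes that sum to the total.

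2. In section 10.3.2, pre-specify city and enrolment period (before or after the change) as covariates in the LTMLE regressions, and use the period-specific randomisation probabilities. City belongs there because it is the stratification factor.

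3. Only if some period enrolled to Text alone, base the primary Text versus Info and Text versus App comparisons on concurrently randomised participants, with the full set as a sensitivity analysis. Apply the same rule to Secondary Aim 4, which makes the same between-arm contrasts. Keep every Text participant for Secondary Aim 3 ("Determine the added benefit of text messaging plus eCoaching versus text messaging alone"), because its 2:1 re-randomisation is within arm and needs no concurrent Info or App participants.

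The cost is protocol wording, two named covariates and probabilities that the trial already knows. If the ratio merely changed, nobody is excluded, and the standard error of Text versus Info rises by under 2% for m up to 60 and under 5% for m up to 80. In the Text-only case, 25 of 108 Text participants (23%) leave the primary Text comparisons and the standard error rises by about 6%.
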